3.2.1 Inclusion Criteria

To be considered eligible to participate in this study, a subject must meet the inclusion criteria listed below:

- 1. Male or female between 18 and 75 years of age;
- 2. Have a clinical diagnosis of PSC as evident by chronic cholestasis of more than six months duration with either a consistent magnetic resonance cholangiopancreatography (MRCP) or endoscopic retrograde cholangiopancreatography (ERCP) showing sclerosing cholangitis;
- 3. If subjects have Inflammatory Bowel Disease (IBD) they will be eligible to participate. If a subject has IBD, documented evidence of IBD must have been evident by prior endoscopy or in previous medical records for ≥6 months. In addition, subjects may only enter the study with a Partial Mayo Score of 0-4, inclusively. Subjects who are on treatment are allowed, provided they are stable for 3 months if taking:
 - i. 5-amino salicylic acid drugs,
 - ii. azathioprine,
 - iii. 6-mercaptopurine, or methotrexate
 - iv. biologics;
- 4. Have a serum ALP $\geq 1.5 \times$ upper limit of normal (ULN);
- 5. Females of child-bearing potential and males participating in the study must either agree to use at least 2 approved barrier methods of contraception or be completely abstinent from sexual intercourse, if this is their usual and preferred lifestyle, throughout the duration of the study and for 3 months after stopping

- study drug. Females who are postmenopausal must have appropriate documentation;
- 6. Be able to understand and sign a written informed consent form (ICF);
- 7. Subjects receiving allowed concomitant medications need to be on stable therapy for 28 days prior to the Baseline visit, with the exception of UDCA, which should be stable for at least 6 weeks prior to the Baseline visit.

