3.3.2 Safety

Safety endpoints to be used in this study will include:

- 1. Proportion of subjects with a treatment-emergent adverse event (TEAE) or a clinically significant laboratory abnormality (overall and of any given type);
- 2. Proportion of subjects who discontinue due to an adverse event (AE) (either treatment-emergent or clinically significant laboratory abnormality).

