6.9 LIVER ADVERSE EVENTS

The following algorithm will be used to monitor for drug-induced liver injury (DILI):

If isolated transaminase (AST or ALT) elevations are observed, defined as: Normal bilirubin and absence of clinical hepatitis, AND

- 1. ALT or AST \geq 5 times the ULN if normal at baseline, OR
- 2. ALT or AST \geq 3 times the baseline or \geq 400 U/L if abnormal at baseline

Then

- 1. Repeat liver profile (ALT, AST, bilirubin and PT/INR) within 2 to 3 days, AND
- 2. Monitor the patient with laboratory testing and physical examination 2 to 3 times per week as per the "close observation" definition in the DILI guidance (https://www.fda.gov/downloads/Drugs/.../Guidances/UCM174090.pdf).

If any ONE of the following criteria is met:

- Transaminases (ALT or AST \geq 3 x baseline) AND bilirubin (total bilruibin \geq 2 x ULN), OR
- Cholestatic markers (ALP or GGT > 2 x baseline), OR
- Isolated ALT/AST ≥ 8x ULN or 600 U/L in the presence of normal CPK and LDH and not secondary to cholangitis, OR
- INR increase > 1.5 refractory to vitamin K administration

OR: if any ONE of the following criteria is met for total bilirubin unrelated to hemolysis:

- 1. Doubling of total bilirubin
 - OR: any increase in total bilirubin if there are symptoms of clinical hepatitis (e.g., vomiting, nausea, right upper quadrant pain),
 - OR: there are immunological reactions (rash or >5% eosinophilia),

Then

- 1. study medication must be interrupted, and
- 2. a drug-induced liver injury workup must be initiated for alternate etiologies;
- 3. repeat a liver profile (ALT, AST, total bilirubin, direct bilirubin, ALP) and PT/INR within 48 to 72 hours;
- 4. monitor the patient with further laboratory testing and physical examination 2 to 3 times per week as per the "close observation" definition in the DILI guidance (https://www.fda.gov/downloads/Drugs/.../Guidances/UCM174090.pdf.
- 5. If a subject lives in a remote area, they can be tested locally and the results communicated to the investigator promptly.

Rechallenge

- 1. Only if a firm alternate etiology is identified AND liver tests have returned to baseline (a rechallenge may be considered)
- 2. If cholangitis is the etiology diagnosis must be firmly established according to the protocol definition before a rechallenge is considered

Rechallenge is not recommended if it is determined that the subject has had a drug induced liver injury.

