8.2.4 Safety Analysis

The safety population will be used for all safety analyses. AE data will be listed individually, and the incidence of adverse events will be summarized by system organ class and preferred terms within a system organ class for each treatment group. When calculating the incidence of AEs, each AE will be counted only once for a given subject within a specified system organ class, preferred term. If the same AEvent occurs on multiple occasions for a subject, the occurrence with the highest severity and relationship to study drug will be reported. If two or more AEs are reported as a unit, the individual terms will be reported as separate events.

Changes in vital signs, hematology, and clinical chemistry parameters from Baseline to the end of the study will be examined. Treatment-emergent changes from normal values to abnormal values in key laboratory parameters will be identified.

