5.3.2. Clinical Laboratory Assessments, Vital Signs, Height, and Weight

Descriptive summaries of selected (quantitative) clinical laboratory results and change from Baseline will be presented by time point and overall treatment groups. Baseline will be the last value observed prior to dosing in Period 1. For more detail on how safety tables will be presented, see [Section 3.3.6](#).

Shift tables (low, normal, high) for change from Baseline to Week 6 in Period 1, and from Week 6 to Week 12 in Period 2 will be presented for all appropriate clinical laboratory parameters by treatment group in Period 1 and Period 2 (excluding efficacy only groups).

Descriptive summaries and change from Baseline in vital signs data, as well as height and weight, will be presented by time point and overall treatment groups, similar to the presentation of clinical laboratory assessments.

Values for all safety variables will be listed by subject and visit (as applicable).

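### The SAP's laboratory shift tables cannot show worsening of liver tests that start above the normal range, and they omit Period 3; no table counts subjects by measured liver threshold

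*SAP*

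**What the plan says.** SAP 5.3.2 describes three laboratory displays.

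- Continuous summaries: "Descriptive summaries of selected (quantitative) clinical laboratory results and change from Baseline will be presented by time point and overall treatment groups".
- Shift tables: "Shift tables (low, normal, high) for change from Baseline to Week 6 in Period 1, and from Week 6 to Week 12 in Period 2", which "will be presented for all appropriate clinical laboratory parameters by treatment group in Period 1 and Period 2 (excluding efficacy only groups".
- Listings: "Values for all safety variables will be listed by subject and visit (as applicable".

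On the protocol side:

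- Section 3.2.1, criterion 4: "Have a serum ALP $\geq 1.5 \times$ upper limit of normal (ULN".
- Section 3.2.2 excludes AST or ALT above 5 x ULN, total bilirubin above 1.2 x ULN, INR above 1.2 and albumin below 3.0 g/dL. No GGT limit is set.
- Section 3.3.2, first safety endpoint: "Proportion of subjects with a treatment-emergent adverse event (TEAE) or a clinically significant laboratory abnormality (overall and of any given type".
- Section 6.9 interrupts study drug on several liver criteria, among them "Cholestatic markers (ALP or GGT > 2 x baseline), OR".
- Section 8.2.4 examines chemistry changes through the end of the study and adds: "Treatment-emergent changes from normal values to abnormal values in key laboratory parameters will be identified".

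SAP section 7 lists changes to secondary efficacy endpoints only. It declares no change to the laboratory safety analysis.

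**The concern.** A low/normal/high shift table registers a change only when a value crosses a reference limit. This population is selected for having one liver test well above its limit, and transaminases may enter above theirs. For those tests the table has no category left in which to record a rise.

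Period 3 is the only placebo-controlled period besides Period 1, and it has no shift table. A value that peaks at Week 2 or 4 and recovers by Week 6 leaves no trace in the Period 1 table. Safety is a secondary objective in patients with liver disease and the arms are small, so a few hepatic cases matter and could be lost in visit means. A reader could take an absence of upward ALP shifts as reassurance when the table could hardly have shown one.

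**Working it through.** There is no stated figure to reproduce. The check places the protocol 6.9 limits into the SAP's categories across the baselines that entry allows.

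**Rule.** Let b be baseline in multiples of ULN. A value is high if above 1 and otherwise normal.

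| Limit in protocol 6.9 | Baseline b (x ULN) | Value at the limit (x ULN) | Shift cell |
|---|---|---|---|
| ALP > 2 x baseline | 1.5 / 2 / 3 | > 3.0 / > 4 / > 6 | high to high |
| ALT or AST ≥ 5 x ULN (normal at baseline) | ≤ 1.0 | ≥ 5 | normal to high |
| ALT or AST ≥ 3 x baseline (abnormal at baseline) | 1.2 / 2 / 4 / 5 | 3.6 / 6.0 / 12.0 / 15.0 | high to high |
| Total bilirubin ≥ 2 x ULN | ≤ 1.0 | ≥ 2 | normal to high |
| Total bilirubin ≥ 2 x ULN | above 1.0 to 1.2 | ≥ 2 | high to high |
| Total bilirubin doubled | ≤ 0.5 | ≤ 1.0 | normal to normal |
| Total bilirubin doubled | 0.6 / 0.8 / 1.0 | 1.2 / 1.6 / 2.0 | normal to high |
| Total bilirubin doubled | 1.1 / 1.2 | 2.2 / 2.4 | high to high |

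GGT above 2 x baseline is also high to high whenever baseline GGT exceeds ULN. Where a shift is visible, its size is not: ALT ending at 1.1 or at 12 x ULN falls in the same normal-to-high cell.

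**Exceptions for ALP.** Protocol 5.1.2 says the central-laboratory Baseline sample is not used for eligibility, so a subject could have fallen into range by then. A subject whose ALP is normal at Week 6 could also shift to high by Week 12.

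**Time points.** Protocol Table 1 schedules chemistry at Weeks 2, 4, 6, 8, 10, 12, 14, 16 and 18, which is 9 post-baseline panels. Weeks 6 and 12 are shift endpoints. The other 9 − 2 = 7 are not, including all 3 in Period 3. For safety tables SAP 5.3.2 refers to SAP 3.3.6, which prefers a scheduled value to an unscheduled one in the same visit. Repeat liver profiles taken under 6.9 can therefore drop out of the summaries, although they remain in the listings.

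**Number of subjects.** SAP 3.2 gives 42 + 17 = 59 randomized. SAP 1.1 reports 3 randomized but not dosed; if they are among the 59, then 59 − 3 = 56 were dosed.

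**The case against.** The strongest reply is that the gap is narrow and other displays cover much of it.

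- *Bilirubin, INR, albumin and normal-baseline transaminases can shift.* This stands. A reader might infer that no liver worsening can appear as a shift. The documents do not support that: the ALP criterion says nothing about the other tests, and the limits on bilirubin, INR and albumin leave room for a shift.
- *Laboratory AEs are tabulated.* SAP 5.3.1 summarizes TEAEs by SOC and PT, by period and by severity. Protocol 5.1.3 to 5.1.5 has laboratory deteriorations at Weeks 6, 12 and 18 recorded as AEs, so it would be wrong to say that only means and listings remain. But this route depends on investigator reporting. The text for the between-visit samples (such as Weeks 2 and 4) carries no such instruction, though the general AE definition includes abnormal laboratory findings. Protocol 6.1 excludes expected disease progression, under which an ALP rise in PSC might go unreported.
- *ALP is examined closely elsewhere.* This also stands. SAP 5.2.2 and 5.2.5 plan individual ALP lines through Week 18. ALP and GGT have mixed models in Period 1, and ALP normalization and bilirubin change are reported for every period. It cannot be said that hepatic safety is unreadable or that ALP worsening is hidden. These are efficacy displays, however, and none counts subjects by arm who crossed a liver limit.
- *The shift tables do what protocol 8.2.4 asks, and 6.9 is a monitoring algorithm.* In part. They give normal-to-abnormal changes at the end of Periods 1 and 2, but not Period 3. Section 6.9 does not define a clinically significant abnormality for analysis, so its limits may be tabulated but must not become that definition.

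**Conclusion.** The concern holds in limited form. The shift tables cannot show worsening of ALP that is already high, or of transaminases or GGT already above ULN. They grade nothing, use period-end values only and omit Period 3. No table counts by arm the subjects who crossed a measured liver limit. The laboratory part of the 3.3.2 endpoint has no dedicated table, and SAP section 7 does not declare this.

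For ALP, essentially none of the 56 to 59 subjects can shift upward from Baseline to Week 6, apart from anyone back in range at Baseline. For transaminases, the share of worsening that would be missed cannot be computed, because the documents do not say how many subjects start above ULN; it could lie anywhere from 0% to 100%. The classification assumes that high means above ULN. The primary efficacy analysis is unaffected. This is a reporting gap that should be closed before the tables are produced.

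**What to change.** In SAP 5.3.2:

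1. Add a Week 12 to Week 18 shift table by the Period 3 groups, setting continued active treatment against withdrawal to placebo.
2. For Periods 1, 2 and 3, by treatment received, add the number and percent of subjects whose worst value in the period, scheduled or unscheduled, met the limits in protocol 6.9. Cover ALT/AST, ALP, GGT, total bilirubin, INR and the ALT/AST-with-bilirubin combination.
3. Keep the 6.9 conditions as written: normal versus abnormal at baseline, the 400 and 600 U/L limits, and the CPK, LDH, cholangitis, hemolysis and vitamin K qualifiers. Table 1 names neither CPK nor LDH, so where a qualifier cannot be derived from the data, count the numeric crossing and footnote it. Take baseline as the last value before Period 1 dosing, as SAP 5.3.2 already defines it.
4. Present these descriptively beside the TEAE tables as supportive laboratory-abnormality tables. They neither redefine clinical significance nor change any clinical rule. Record the addition in SAP section 7.

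The cost is SAP wording and a few more tables from data already collected. The drawback is extra output with small counts.

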After the Week 12 visit, all subjects are eligible to enroll into the 6-week Randomized Withdrawal Period of the study. Subjects who do not wish to continue may choose to discontinue and should be handled according to the information listed in Sections 5.1.6 and Section 7.0.

5.1.5 Random Withdrawal Period, Weeks 14, 16, and 18

During the random withdrawal period, the following procedures and assessments will be conducted on Weeks 14 and 16:

- Subjects are required to provide blood samples for CBC, CMP, and Lipids. This will not require a visit to the study site and will involve local sample collection.
- Subjects will be contacted by the Investigator, or one of their staff, to discuss the occurrence of any AEs, any new or changes in concomitant medications, adherence to the treatment schedule, and compliance with the requirement to visit a pre-specified clinical laboratory for CBC, CMP, and Lipids. Any new medications that are being taken are, by default, to be considered as being necessitated by an AE. If necessary, subjects may be asked to visit the investigational site, at the Investigator's discretion.

• It is recognized that some investigational sites may require subjects to come to the clinic for these visits and related activities.

During the random withdrawal period, the following procedures and assessments will be conducted during the visit to the investigational site on Weeks 18:

- Prior and concomitant medications will be reviewed and any changes will be recorded on the appropriate eCRF page. Generally, any new medications that are being taken are, by default, to be considered as being necessitated by an Adverse Event. Rarely, a previously unmentioned prior medication may be disclosed, and that eCRF page should be updated.
- A physical examination including vital signs will be conducted and any findings that represent clinical deteriorations from Baseline are to be recorded as Adverse Events.
- An ECG is to be recorded. Any findings that represent clinical deteriorations from Baseline are to be recorded as an AE.
- Blood samples for CBC, INR, CMP, and Lipids panel are to be collected and sent to the designated central laboratory. Any subsequent findings that represent clinical deteriorations from Baseline are to be recorded as an AE.
- Partial Mayo Score.
- Subjects with IBD will provide a blood sample for C-reactive protein.

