1.3. GLOSSARY OF ABBREVIATIONS

AE	Adverse Event
ALP	Alkaline Phosphatase
ALT	Alanine Aminotransferase
ANCOVA	Analysis of Covariance
AST	Aspartate Aminotransferase
BID	twice daily
BMI	Body Mass Index
CRF	case report form
CRP	C-reactive Protein
CSR	clinical study report
CTCAE	Common Terminology Criteria for Adverse Events
DSMB	Data and Safety Monitoring Board
ET	Early Termination
FAS	full analysis set
FC	Fecal Calprotectin
GGT	Gamma-Glutamyl Transferase
IBD	Inflammatory Bowel Disease
ITT	Intent-to-treat population
IxRS	interactive web/voice response system
LOCF	Last Observation Carried Forward
MedDRA	Medical Dictionary for Regulatory Activities
mITT	Modified intent-to-treat population
MMRM	Mixed Model with Repeated Measures
PP	per protocol
PSC	Primary Sclerosing Cholangitis
PT	Preferred Term
SAE	serious adverse event
SD	standard deviation
SOC	System Organ Classification
TEAE	treatment emergent adverse events
UDCA	ursodeoxycholic acid
WHO	World Health Organization

2. **OBJECTIVES**

Primary Objective:

The primary objective of this proof-of-concept study is to evaluate the effects of HTD1801 on serum alkaline phosphatase (ALP) levels in adult subjects with PSC.

Secondary Objective:

The secondary objectives of this study are to evaluate:

- the effects on concurrent disease activity of IBD, and
- the safety (inclusive of adverse events, serology, and vital signs) and
- the tolerability of HTD1801 over 18 weeks in adult subjects with PSC.

3. **GENERAL STATISTICAL CONSIDERATIONS**

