Following their completion of Period 1, subjects will enroll in a 6-week extension period in which subjects previously randomized to 500 mg or 1000 mg BID will continue for 6 more weeks at that previous dose, while subjects previously randomized to placebo will be randomly assigned to receive 6 weeks of either 500 mg or 1000 mg BID.

Period 3: Randomized withdrawal

Following their completion of Period 2, subjects will enroll into a 6-week randomized withdrawal period in which all subjects will be randomly assigned in a 1 to 1 ratio to either continue on the active treatment they received in Period 2, or be assigned to placebo so that 50% of the subjects remain on the experimental treatment at the previous dose, and 50% will receive placebo.

All subjects and study personnel will remain blinded as to the treatment administered throughout the study with the exception of an unblinded statistician who will develop the randomization list with the expanded strata and an unblinded EDC designer who will load the completed randomizations

into the EDC system. All study test drug will be provided in matching white tablets, four to a bottle, two bottles to be administered each day, one in the morning and one in the evening. A 45-day supply will be provided to each subject at each visit to cover the next 6-week period with an additional 3 days of coverage to provide for possible scheduling conflicts.

In this double-blind study, if a medical emergency occurs and a decision about a subject's condition requires knowledge of the treatment assignment in order to properly treat the subject, the study blind may be broken for that specific subject only. Ideally, the decision to break the blind for this one subject should only be made after consultation with the Medical Monitor or Sponsor Representative.

Any broken blind must be clearly justified and explained by a note in the subject's source documents.

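### Laboratory shift tables stop at Week 12, so normal-to-abnormal changes in Period 3, or seen only at visits other than Weeks 6 and 12, are not counted

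*SAP*

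**What the plan says.** SAP 5.3.2 provides shift tables (low, normal, high) "for change from Baseline to Week 6 in Period 1, and from Week 6 to Week 12 in Period 2", laid out by the Period 1 and Period 2 treatment groups. No other SAP section adds a shift table.

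The same section also gives a second output: "Descriptive summaries of selected (quantitative) clinical laboratory results and change from Baseline will be presented by time point and overall treatment groups". Baseline there is the last value before Period 1 dosing. All safety values are listed by subject and visit.

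The commitments and data behind these outputs are:

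- **Objective (SAP 2).** It includes "the tolerability of HTD1801 over 18 weeks in adult subjects with PSC".
- **Protocol 8.2.4.** "Changes in vital signs, hematology, and clinical chemistry parameters from Baseline to the end of the study will be examined". The next sentence undertakes to identify changes from normal to abnormal that arise on treatment in key laboratory parameters, with no time limit.
- **Sampling (Protocol 5.1.5).** For Weeks 14 and 16: "Subjects are required to provide blood samples for CBC, CMP, and Lipids", by local collection. For Week 18: "Blood samples for CBC, INR, CMP, and Lipids panel are to be collected and sent to the designated central laboratory".
- **Period 3 (SAP 3.2).** "all subjects will be randomly assigned in a 1 to 1 ratio to either continue on the active treatment they received in Period 2"; the alternative is placebo.
- **Visit windows (SAP 3.3.6).** Unscheduled and early-termination values are assigned to a visit by study day. Days 21 to 34 become Week 4 and Days 63 to 76 become Week 10.

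**The concern.** A shift table is the output that turns individual laboratory values into a count of subjects who left the normal range. Here that count ends six weeks before treatment does. Period 3 is where longer exposure would show itself, and where subjects who continue can be set against subjects randomised at the same time to placebo. A subject first out of range at Week 14, 16 or 18 appears in no shift table.

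The tables also compare single visits. A value that is abnormal only at Week 2, 4, 8 or 10 does not enter them. Nor does the final value of a subject who stops on Day 30 or Day 70, and subjects who stop because of a laboratory abnormality are among those a safety reader most wants counted.

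**Working it through.** The plan states no figure for this point. The check compares what is collected with what is tabulated, then sizes the group affected.

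**1. Coverage.** Post-Baseline laboratory draws (Protocol Table 1; SAP 1.2) fall at Weeks 2, 4, 6, 8, 10, 12, 14, 16 and 18, nine in all. The post-Baseline visits used by the shift tables are Weeks 6 and 12, so two of nine. The tables span Weeks 0 to 12 of 18, leaving 6/18 = 33% of the planned treatment time without one. Only the first table starts from the pre-treatment value; the second restarts at Week 6.

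**2. Early stops (SAP 3.3.6).** Day 30 lies in 21 to 34, so it is Week 4. Day 70 lies in 63 to 76, so it is Week 10. Neither visit feeds a shift table. An early-termination value enters only if it falls in the Week 6 or Week 12 window.

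**3. Subjects in Period 3.** Inputs are 1:1:1 allocation in Period 1 (SAP 1.1), 1:1 in Period 3 (SAP 3.2), and full completion (an assumption). For N subjects:

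- on active drug in Period 3 = N/2
- active for 18 continuous weeks = N × 2/3 × 1/2 = N/3
- Period 1 placebo subjects still active at Week 18 (12 weeks on drug) = N × 1/3 × 1/2 = N/6
- withdrawn to placebo = N/2

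Three values of N bracket the trial. SAP 3.2 gives 42 + 17 = 59 randomised. SAP 1.1 says 3 randomised subjects had not started dosing, which gives 56 if they are among the 59. SAP 3.1 gives 63 as the revised target.

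| N | Active in Period 3 | 18 continuous weeks | 12 weeks (switchers) | Withdrawn to placebo |
|---|---|---|---|---|
| 56 | 28.0 | 18.7 | 9.3 | 28.0 |
| 59 | 29.5 | 19.7 | 9.8 | 29.5 |
| 63 | 31.5 | 21.0 | 10.5 | 31.5 |

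**4. Do the other outputs supply the count?**

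- The by-visit summaries cover selected parameters. SAP 5 defines descriptive statistics as n, mean, median, SD, minimum and maximum, so an extreme value shows but the number of subjects out of range does not. The overall groups follow actual treatment at the visit, so at Week 18 each dose column mixes subjects with 18 and with 12 weeks on drug.
- Listings show every value and count nothing.
- Adverse event tables count a laboratory finding only if it was recorded as an adverse event. Protocol 5.1.5 asks for this at Week 18 when the finding is a clinical deterioration from Baseline.
- The ALP, GGT and bilirubin endpoints (SAP 5.2.4) reach Week 18 by Period 3 group. For GGT and bilirubin they are changes in value. The ALP responder proportions count improvement, not worsening.

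**The case against.** The case on the other side is substantial, and most of it stands.

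- **The safety objective is not abandoned after Week 12.** By-visit summaries with minimum and maximum, listings, adverse events by period (SAP 5.3.1), the ALP, GGT and bilirubin summaries and the individual ALP plots all run to Week 18. A reader might infer from the shift tables alone that the 18-week objective goes unanswered for laboratory data. The documents do not support that.
- **Protocol 8.2.4 does not ask for shift tables.** Its commitment on change from Baseline is met by the by-visit summaries. Its commitment on normal-to-abnormal change is limited to key parameters and says they will be identified, which listings and adverse event capture can arguably do. It is tempting to call this a departure that SAP 7 should have recorded, but the text does not establish one.
- **The Week 6 restart does not hide a sustained abnormality.** A subject who goes from normal to high by Week 6 and stays high is a shift in the first table and high-to-high in the second. For placebo subjects who switch at Week 6, that visit is the right pre-active reference.
- **Period 3 placebo subjects are used.** They form the placebo column of the by-visit summaries at Weeks 14 to 18. Only the shift tables omit them.
- **The numbers are small.** Roughly ten subjects per dose reach 18 weeks, so a listing can be read by eye, and the SAP provides for a DSMB.

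None of these outputs counts subjects who move out of range after Week 12, or those whose abnormal value falls only at a visit outside the two tables. Reading a listing by eye gives no defined count by treatment group.

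**Conclusion.** The point holds as a gap in tabulation. Categorical laboratory shifts are counted for two intervals ending at Week 12. They are not counted for Period 3, nor for values seen only at other visits or at early terminations windowed to those visits. The identification of normal-to-abnormal changes in Protocol 8.2.4 therefore has no tabulated form after Week 12. The conclusion goes no further than that: laboratory safety to Week 18 is reported in other ways, and the primary analysis is untouched.

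The group concerned is about 28 to 32 subjects on active drug in Period 3, of whom about 19 to 21 would have 18 continuous weeks. About 28 to 32 more are withdrawn to placebo. These figures assume 56 to 63 subjects, exactly equal allocation and full completion; dropout would lower them. The textual finding depends on none of these assumptions. The change is worth making because the data are already scheduled and the Period 3 groups are already defined.

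**What to change.** In SAP 5.3.2 keep the two existing tables and add two.

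1. **Week 12 to Week 18 shifts**, by the Period 3 treatment groups already listed in SAP 5. This sets continued drug against concurrent randomised withdrawal.
2. **Last value before first active dose to worst value on active drug through Week 18.** The reference is Baseline for subjects on active drug in Period 1 and Week 6 for placebo switchers. Include unscheduled and early-termination values. For subjects withdrawn to placebo, close the on-drug window at the end of Period 2. Class each value against the reference range of the laboratory that ran it, because Weeks 2, 4, 8, 10, 14 and 16 use local collection while Weeks 6, 12 and 18 go to the central laboratory.

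The cost is two tables and no new data. Worst-value counts will look slightly less favourable than single-visit counts. They also rise with the number of draws: scheduled on-drug draws run from 3 (switchers then withdrawn: Weeks 8, 10, 12) to 9 (continuous active). No placebo group has equal duration, so table 2 should be labelled descriptive.
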